## Costs and Reimbursement

### 1. Costs to subjects

There are no costs to the subjects for participating in this study.

## 2. Honorarium

Subjects will receive an honorarium of \$150 after completing the baseline, 3 month and 6 month follow-up visits (for a total of \$450). A limited amount of travel money is also available.

## Data and Safety Monitoring Plan

### 1. Reporting of adverse events

The study will comply with Food and Drug Administration (FDA) regulations requiring expedited reporting of any adverse events (AE) that are serious, unexpected and associated with the use of a study drug. All serious adverse events will be reported within 24 hours to the IRB, DSMB, Independent Medical Monitor, and FDA.

Adverse events must be recorded starting from the time of informed consent until the final study visit. Any medical condition present at the initial visit, which remains unchanged or improves, should not be recorded as an adverse event at subsequent visits. However, if there is **deterioration** of a medical condition that was present at the initial visit, this should be considered a **new** adverse event and reported. All adverse events (AEs), whether or not they are considered related to the study, shall be recorded on the Case Report Forms (CRFs).

Clinically significant changes (abnormalities), in the judgment of the investigator, in physical examination from the baseline exam will be recorded as an adverse event.

The following information must be collected and recorded for each AE:

- AE term (diagnosis)
- Start date of AE
- Stop date of AE
- Severity of AE (mild, moderate, or severe)
- Seriousness of AE (serious or non-serious)
- Action taken regarding study medication (none, study medication dose reduced, study medication interrupted, or study medication stopped);
- Action taken regarding AE (specific treatment instituted, subject hospitalized, etc.)
- AE outcome (resolved, ongoing, death, or lost to follow-up)
- AE causality (none, possible, probable)

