#### **Study Time Line and Procedures:**

Patients will receive three in-person evaluations during this study. An outline of the testing that will take place during these visits is provided in **Schedule 1 (attached)**.

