- Placement of a 12-lead 24-hour Holter monitor test. The patient will come to the University of Rochester Clinical Research Center (CRC) and a technician from the Cardiology Group working on this project will work with the CRC nursing staff to set up the Holter monitor. Patients will not require this testing if they have had a Holter monitor within 2 months. This testing can be done before or after the above screening procedures and after the screening consent form has been reviewed and signed.

**Potential Enrollment: All screening information will be reviewed by the PI to determine subject eligibility. If a patient satisfies all the inclusion and exclusion criteria, the patient will be invited to participate in the research study and a consent form for the treatment trial (attached) will be reviewed with them. If the patient decides to participate in the clinical trial the patient will undergo the following:**

- I. Continuation of the Screening/Baseline Visit at the University of Rochester Clinical Research Center (CRC). This visit will take two days. During this visit a series of evaluations will be carried out to determine how the patient is affected by myotonic dystrophy. An additional aspect of the Screening/Baseline Visit is that the patient will be started and monitored on the study drug (either mexiletine or placebo).

- II. Follow-up visits to the CRC 3 months and 6 months after the Screening/Baseline Visit. During these visits many of the same evaluations from the Screening/Baseline Visit will be repeated to determine how the patient's condition has changed over time.
- III. Telephone evaluations. The patient will receive a telephone call about every two weeks while they are enrolled in the study, except for the weeks when they come to the CRC for a study visit. The study coordinator will telephone the patient to check on any side effects that may occur and make sure that the study medication is being taken as directed. The coordinator will also ask each patient about their pain level during these phone calls.

A schedule of procedures and assessments for this project is outlined in **schedule 1** (Appendix C).

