### **Itinerary of Follow-up Visits: (Month 3 and Month 6)**

The evaluations of patients at their Month 3 and Month 6 Visits will be similar to those performed at their Screening/Baseline Visit with the exception that a DEXA scan will only be performed at Screening/Baseline and at Month 6. Holter monitoring will occur within the week immediately before the CRC admissions at Month 3 and Month 6, and the procedure for placement of the Holter recording equipment and electrode placement will use the same standard procedure described above and routinely used by our cardiology consultant group at the University of Rochester Medical Center.

On the Month 3 and Month 6 follow-up visits, the patient will complete the following study procedures following an overnight fast. The patient will be supplied with a standard breakfast after the blood draw.

- An electrocardiogram will be performed.
- The patient will have up to 4 tablespoons of blood drawn, and if the patient is a female of childbearing potential, a pregnancy test will be done. A urine sample will be collected to test kidney function.
- A study doctor will perform a history and physical examination; height, weight and vitals will be recorded.
- A study doctor and study coordinator will discuss any side effects that the patient may have experienced and any recent changes in medications.
- An assessment of the 6-minute walk test (6MWT) will be performed.
- A swallowing evaluation will be conducted.
- Myotonia, functional, and strength testing will be performed (as described above).
- A standard lunch will be given on the CRC.
- A DEXA study will be performed (six month only).
- Questionnaires will be completed (Upper Extremity Functional Index, myotonia visual analog scale, Medical Outcome Short Form Health Survey (SF 36), Epworth Sleepiness Scale, an Individualized Neuromuscular Quality of Life Questionnaire (INQoL), two gastrointestinal function questionnaires, chronic pain scale and brief pain inventories, and a DM1 specific Health related quality of life questionnaire (MDHI). Additionally, patients will be asked to complete an assessment of the usability and relevance of some of these questionnaires (i.e., SF-36, INQoL, and MDHI).
- The study coordinator will collect medication bottles, unused medication and the patient's diary. At the month 3 visit, the patient will be provided with a new supply of study medication and a patient diary.
- The patient will receive a standard dinner on the CRC.

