### **Coordination of Patient Care Following the Completion of the Study Protocol:**

At the completion of the study all patients will be tapered off the study drug/placebo over a one week period. We will provide each patient's primary care physician and/or neurologist a detailed summary of the patient's current health status and will coordinate with them any questions regarding management of their patient including the potential use of mexiletine therapy.

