### **Study Testing Procedures:**

#### Evaluation of safety and tolerability:

Adverse side effects will be monitored during each CRC visit (Baseline, Month 3, Month 6) and during telephone calls at about 2 week intervals during the intervening weeks of the trial. The adverse effects of mexiletine observed most commonly include: dizziness, lightheadedness, nervousness, nausea, vomiting, or upset stomach, diarrhea, constipation, trembling, shaking of hands, blurred vision, tiredness, or weakness. More serious side effects, which are less common include: irregular heart beat, chest pain, shortness of breath, trouble breathing, skin rash, severe itching, or hives.

If there are more serious side effects, the principal investigator will be notified. The principal investigator will contact the patient and determine if it is necessary to have the patient reduce the dosage of treatment agent or to stop it. The principal investigator will also determine if an urgent evaluation of the patient is necessary. These medical plans and any related change in care will be coordinated with the primary care physician of the patient. If necessary, the code will be broken to determine if the patient is receiving placebo or mexiletine treatment.

Additional details regarding the evaluation of the safety and tolerability of this medication are provided in the human subjects section of this application.

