#### Analysis of Safety Outcomes and Subject Disposition:

Adverse events will be tabulated by treatment group, severity, and perceived relationship to study drug. For each adverse event (AE), the treatment groups will be compared regarding the occurrence of at least one event using Fisher's exact tests. The comparisons will be repeated excluding all mild symptoms. Particular attention will be paid to AEs known to be associated with mexiletine in previous studies. Individual AEs will be listed, with particular attention paid to serious AEs. Laboratory test abnormalities will be similarly analyzed, whether or not they are judged to be clinically significant (classified as AEs).

Continuous measures of safety (vital signs, EKG results, laboratory test results) will be analyzed descriptively. Formal analyses may be performed using methods similar to those described above for the primary outcome variable (repeated measures analysis of covariance).

The frequency of and reasons for subject withdrawal, dosage reduction, and premature withdrawal of study drug will be summarized by treatment group. The compliance data (amount of unused drug returned, compliance diaries) will be summarized by treatment group and visit, as will dosage level of study drug. Guessed treatment from the blindness questionnaire will be tabulated by actual treatment separately for subjects and the investigator. Chi-square tests will be used to determine whether or not the proportion of subjects who guess that the subject received mexiletine treatment differ among the actual treatment groups. The investigator's guesses will be similarly analyzed. Additional information regarding adverse event assessment and processing is provided in the Human Subjects Protection portion of this application.

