### **Probable**

- The event follows a reasonable temporal sequence from the time of drug administration,
- **And** follows a known response pattern to the study drug,
- **And** cannot be reasonably explained by other factors such as the subject's clinical state, therapeutic interventions, or concomitant drugs administered to the subject,
- **And** either occurs immediately following trial drug administration, **or** improves on stopping the drug, **or** reappears on repeat exposure, **or** there is a positive reaction at the application site.

**Severity of an adverse event** is defined as a qualitative assessment of the degree of intensity of an adverse event as is determined by the investigator or reported to him/her by the subject.

The assessment of severity is made irrespective of drug relationship or seriousness of the experience and should be evaluated according to the following scale:

**1 = Mild**– The adverse event is easily tolerated and does not interfere with daily activity.

**2 = Moderate**– The adverse event is not easily tolerated and interferes with daily activity.

**3 = Severe**– The adverse event is incapacitating and the subject is unable to function.

Adverse side effects will be monitored during each CRC visit (baseline, month 3, month 6) and during telephone calls at about 2 week intervals during the intervening weeks of the trial. The adverse effects of mexiletine observed most commonly include: dizziness, lightheadedness, nervousness, nausea, vomiting, or upset stomach, diarrhea,

constipation, trembling, shaking of hands, blurred vision, tiredness, or weakness. More serious side effects, which are less common include: irregular heart beat, chest pain, shortness of breath, trouble breathing, skin rash, severe itching, or hives.

The laboratory studies will provide additional evidence of any major organ toxicity. Patients will also receive a diary to record adverse events as they occur as well as a schedule to remind them to take the study medication.

The following definitions will be utilized:

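### Adverse event recording stops at the Month 6 visit, but every patient then takes study capsules through a one-week taper that no planned collection of non-serious events covers

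*Combined protocol and SAP*

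**What the plan says.** The recording window is set in the Data and Safety Monitoring Plan, item 1 (Reporting of adverse events): "Adverse events must be recorded starting from the time of informed consent until the final study visit." Study Time Line and Procedures fixes the number of visits: "Patients will receive three in-person evaluations during this study." These are Screening/Baseline, Month 3 and Month 6, so the final visit is Month 6.

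The section on coordinating care after completion of the protocol then says: "At the completion of the study all patients will be tapered off the study drug/placebo over a one week period."

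The other routes for finding events are these:

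- **Telephone calls.** Screening Evaluations, item III: "The patient will receive a telephone call about every two weeks while they are enrolled in the study." Evaluation of safety and tolerability places the calls in the weeks between the visits.
- **Diary.** The text after the causality definitions says: "Patients will also receive a diary to record adverse events as they occur." Itinerary of Follow-up Visits has the diary, bottles and unused drug collected at the follow-up visits. For Month 3 only, it adds that "the patient will be provided with a new supply of study medication and a patient diary."
- **Serious events.** These are to be reported within 24 hours, with no end date given.

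In the analysis of safety outcomes, for each type of adverse event, "the treatment groups will be compared regarding the occurrence of at least one event."

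**The concern.** The taper is dosing with blinded study product that the protocol directs for all patients, yet it falls outside the period in which adverse events must be recorded. Safety and tolerability is the first secondary aim. The planned comparison of arms is binary for each event type, so a patient whose first event of a given type occurs in the taper week is counted as having had none.

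There is a second consequence. The protocol asks for a stop date and an outcome for every event, and improvement on stopping the drug is one of the alternative criteria for calling an event probably related. For patients who finish on treatment, the taper is the planned discontinuation. Because recording ends before it, an event still present at Month 6 has no planned follow-up to show whether it resolved off drug.

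**Working it through.** The plan gives no figure to reproduce here. The check sets the recording window against the dosing period and then sizes the uncovered part.

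**Timeline**

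1. Recording ends at the final study visit. With three visits, that is Month 6.
2. The taper follows Month 6. Its section places it at completion of the study, and the section on cardiac conduction describes the Month 6 Holter data as collected on therapy.
3. Telephone calls are tied to enrollment and to the weeks between visits. Even if a tapering patient still counts as enrolled, a call about every two weeks need not fall in a one-week taper.
4. The diary is collected at Month 6, and no replacement is described.
5. Overlap of planned non-serious event collection with the taper: 0 of 7 days.

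**Size of the gap**

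Inputs:
- Taper of 1 week.
- Treatment of six months, taken as 26 weeks (assumption).
- 20 patients per arm, or 18 with the 10% withdrawal allowed for under Sample Size Considerations. That section also says enrollment will be raised as needed to reach a final 20 per arm, so 18 to 20 spans both statements.

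Share of time on study drug: 1/(26 + 1) = 1/27 = 3.7%.

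| Patients per arm | Taper patient-weeks | Total patient-weeks on drug | Share |
|---|---|---|---|
| 20 | 20 × 1 = 20 | 20 × 27 = 540 | 3.7% |
| 18 | 18 × 1 = 18 | 18 × 27 = 486 | 3.7% |

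Both arms together: 36 to 40 patient-weeks, partly at reduced dose.

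**What a closing call would add**

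If no event of a given type is found among n mexiletine patients, the one-sided 95% upper bound on the taper-week risk solves (1 − p)^n = 0.05, so p = 1 − 0.05^(1/n).

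- n = 20: 1 − 0.05^(1/20) = 13.9%
- n = 18: 1 − 0.05^(1/18) = 15.3%

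This is modest information, but as described the plan would support no estimate.

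**The case against.** The best case for the plan has four parts.

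**Unseen documents.** Schedule 1 (Appendix C) and the Manual of Operations are cited but are not in the available text. Either could list a contact after the taper, and the rule that calls continue while patients are enrolled could be read to include the taper. This stands as a limit on saying that no contact is planned. It does not change the recording rule, which would still end at the final visit.

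**Scope of the aim.** The safety aim refers to six months of therapy, and the taper sits under care after completion of the protocol. On that reading, a patient whose first event falls in the taper is correctly event-free over six months. That is a coherent choice for the between-arm comparison. It does not justify leaving events unrecorded while patients take investigational product on the protocol's instruction; taper events can be recorded and summarized separately if the six-month comparison is to be kept.

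**Serious events are protected.** The 24-hour rule has no end date, the medical monitor follows each serious event to an endpoint, and the treating physicians receive a summary at completion. This is right, and it confines the gap mainly to non-serious events, although no scheduled contact is described that would bring a serious event to light during the taper.

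**Small size.** The gap is 3.7% of dosing time, no withdrawal hazard is established, and even a clean result would leave an upper bound near 14% to 15%. All true. These facts limit the importance of the point; the remedy is correspondingly small.

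**Conclusion.** The concern holds. Followed as written, the plan closes adverse event recording about one week before patients stop taking study capsules, leaving 36 to 40 patient-weeks without planned collection of non-serious events. The loss is in completeness of the safety data. No change in a between-arm safety conclusion has been shown, and the primary analysis is unaffected.

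The conclusion rests on two well-supported readings: that the final study visit is Month 6, and that the taper starts after it. The size rests on taking six months as 26 weeks and on 18 to 20 patients per arm reaching the taper. A contact listed in Schedule 1 or the Manual of Operations would narrow the practical gap, but the recording rule would still need correcting. This should be changed because it bears on a stated aim and costs very little.

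**What to change.** In Reporting of adverse events, move the end of the recording window from the final study visit to the end of the one-week taper. Add one coordinator telephone call at that point, following the procedure already used for the two-weekly calls, to ask about new events and about events still open at Month 6.

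As a minor clarification in Itinerary of Follow-up Visits, state that taper capsules are dispensed at Month 6 after the assessments, since the section has unused drug collected at that visit and describes no taper supply.

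The cost is protocol wording and one call per completing patient, at most 40 calls with 20 per arm. Visits, sample size and the primary analysis stay as they are.

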### **Relationship to study drug:**

The investigator, using the following explanations, will determine study drug relationship for each adverse event:

### **None**

The event is clearly related to other factors such as the subject's clinical state, therapeutic interventions, or concomitant drugs administered to the subject.

### **Possible**

- The event follows a reasonable temporal sequence from the time of drug administration,
- And/or follows a known response pattern to the trial drug, but could have been produced by other factors such as the subject's clinical state, therapeutic interventions, or concomitant drugs administered to the subject.

### **Probable**

- The event follows a reasonable temporal sequence from the time of drug administration,
- **And** follows a known response pattern to the study drug,
- **And** cannot be reasonably explained by other factors such as the subject's clinical state, therapeutic interventions, or concomitant drugs administered to the subject,
- **And** either occurs immediately following trial drug administration, **or** improves on stopping the drug, **or** reappears on repeat exposure, **or** there is a positive reaction at the application site.

**Severity of an adverse event** is defined as a qualitative assessment of the degree of intensity of an adverse event as is determined by the investigator or reported to him/her by the subject.

The assessment of severity is made irrespective of drug relationship or seriousness of the experience and should be evaluated according to the following scale:

**1 = Mild**– The adverse event is easily tolerated and does not interfere with daily activity.

**2 = Moderate**– The adverse event is not easily tolerated and interferes with daily activity.

**3 = Severe**– The adverse event is incapacitating and the subject is unable to function.

Adverse side effects will be monitored during each CRC visit (baseline, month 3, month 6) and during telephone calls at about 2 week intervals during the intervening weeks of the trial. The adverse effects of mexiletine observed most commonly include: dizziness, lightheadedness, nervousness, nausea, vomiting, or upset stomach, diarrhea,

constipation, trembling, shaking of hands, blurred vision, tiredness, or weakness. More serious side effects, which are less common include: irregular heart beat, chest pain, shortness of breath, trouble breathing, skin rash, severe itching, or hives.

The laboratory studies will provide additional evidence of any major organ toxicity. Patients will also receive a diary to record adverse events as they occur as well as a schedule to remind them to take the study medication.

The following definitions will be utilized:

**An adverse event** is any untoward medical occurrence in a subject that occurs during the conduct of a clinical study of a pharmaceutical product that does not necessarily have a causal relationship to the study drug. This can, therefore, be any unfavorable and unintended physical sign, symptom, laboratory parameter, or disease entity that develops or worsens in severity during the course of the study, whether or not considered related to the study drug.

**A serious adverse event (SAE)** is defined as any adverse drug experience occurring at any dose that results in any of the following outcomes:

- Results in death,
- Is life-threatening (NOTE: The term "life-threatening" in the definition of "serious" refers to an event in which the subject was at risk of death at the time of the event; it does not refer to an event which hypothetically might have caused death if it were more severe.),
- Results in inpatient hospitalization or prolongation of existing hospitalization,
- Results in a permanent disability,
- Results in a congenital anomaly/birth defect,
- A new malignancy,
- Overdose, suspected or confirmed.

Important medical events that may not result in death, be life-threatening, or require hospitalization may be considered a serious adverse drug experience when, based upon appropriate medical judgment, the event may jeopardize the patient or subject and may require medical or surgical intervention to prevent one of the outcomes listed in this definition.

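### The causality scale cannot rate a new type of toxicity as Probable, leaves some events unrated, and lets events before the first dose be rated Possible

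*Combined protocol and SAP*

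**What the plan says.** The scale is in Section E, Data and Safety Monitoring Plan, under Relationship to study drug. The investigator applies it to every adverse event, and the list of items to be recorded allows three answers only.

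- **None:** "The event is clearly related to other factors such as the subject's clinical state", or to other treatment.
- **Possible:** two bullets. The first is reasonable timing after dosing. The second, introduced by *and/or*, is that the event "follows a known response pattern to the trial drug, but could have been produced by other factors".
- **Probable:** four conditions, each joined to the last by a bolded *and*. They are "The event follows a reasonable temporal sequence from the time of drug administration"; it "follows a known response pattern to the study drug"; it "cannot be reasonably explained by other factors such as the subject's clinical state, therapeutic interventions, or concomitant drugs administered to the subject"; and one item from a list of supporting features, among them that the event "reappears on repeat exposure".

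Under Reporting of adverse events, recording starts at consent. Under Description of study procedures, the first dose follows completion of the baseline assessments, with dinner on Day 1.

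The rating is used in Analysis of Safety Outcomes and Subject Disposition: "Adverse events will be tabulated by treatment group, severity, and perceived relationship to study drug". The regulatory standard cited in the reporting section is "expedited reporting of any adverse events (AE) that are serious, unexpected and associated with the use of a study drug". No section says which ratings count as associated.

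**The concern.** A causality scale should give each event one rating, and stronger evidence should lead to a stronger rating. This scale fails on both counts.

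Because the known pattern is compulsory, reappearance on re-exposure counts only for effects already recognised. The strongest case-level evidence cannot lift a new type of event to the top category. In the other direction, the *and/or* in Possible makes timing optional, so a familiar complaint that began before any drug was taken can be rated Possible. Some events match no definition, and the form offers no fourth answer.

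At stake is the accuracy of the safety table by relationship, in what the protocol describes as the first long-term placebo-controlled trial of the drug in this disease; the sponsor's earlier crossover trials gave seven weeks of treatment.

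**Working it through.** The plan gives no figure to reproduce. The check is to write the three definitions as rules and see which events each one admits.

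**Attributes, all taken from the definitions**
- T: reasonable temporal sequence (yes/no)
- K: known response pattern (yes/no)
- O: other explanation (none / could be / clear)
- S: at least one supporting feature from the last Probable condition (yes/no)

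Combinations: 2 × 2 × 3 × 2 = 24.

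**Rules**
- Probable = T and K and (O = none) and S
- None = (O = clear)
- Possible, strict reading (the clause about other factors governs both bullets) = (T or K) and (O = could be or clear)
- Possible, lenient reading (the clause governs the second bullet only) = T, or (K and O = could be or clear)

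**Count**

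| Other explanation | Cells | Strict reading | Lenient reading |
|---|---|---|---|
| Clear | 8 | 8 None | 8 None |
| Could be | 8 | 6 Possible, 2 unrated | 6 Possible, 2 unrated |
| None | 8 | 1 Probable, 7 unrated | 1 Probable, 3 Possible, 4 unrated |
| Unrated | 24 | 2 + 7 = **9** | 2 + 4 = **6** |

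All 6 unrated cells on the lenient reading lack a temporal sequence. The strict reading adds 3 cells that have one (9 − 6 = 3). There is also overlap: of the 8 cells with a clear other cause, the 6 with T or K satisfy Possible as well as None.

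**New type of toxicity** (T yes, K no, O none, S yes through re-exposure). It fails Probable because K is missing, and fails None because no other cause is clear. Strict reading: it also fails Possible, so it has no category. Lenient reading: Possible. Across all 12 cells with K absent, the number rated Probable is 0 on either reading.

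**Event before the first dose** (T no, K yes, O could be, S no), for example nausea or tiredness, both on the protocol's list of common effects. It is Possible on both readings. If another cause is clear, it meets Possible and None together. A pre-dose event without a known pattern and without a clear other cause is unrated.

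**The case against.** The strongest reply is that little depends on this rating.

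- All serious adverse events go to the IRB, DSMB, medical monitor and FDA within 24 hours, whatever their causality.
- The independent medical monitor, not the investigator's rating, determines whether a serious event is unexpected and associated with the drug, and also reviews aggregate adverse events and safety laboratory data.
- The DSMB looks at imbalance between arms, and Fisher's exact tests compare the arms for each event without using the rating.

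All of this stands, and it sets the size of the point. A reader might infer that expedited reporting would miss a new toxicity because of the scale. The documents do not support that: serious events are reported regardless, and association is not tied to Probable.

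Two further inferences should be resisted. An unexpected event is not necessarily one without a known pattern, since it may be unexpected only in severity or frequency; the point is exact only for a toxicity of a new type. Nor must effects appearing after seven weeks be unknown in kind. The protocol cites over 35 years of cardiological use and over fifteen years in non-dystrophic myotonia.

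The cell counts are also weaker than they look. Cells are not frequencies. Three of the 6 unrated cells on the lenient reading pair absent timing with a supporting feature, which will seldom occur. The bullet layout supports the lenient reading at least as well as the strict one. The pre-dose problem rests on literal wording, since a response to a drug naturally implies exposure. Start dates are recorded, the window is short, and neither arm is favoured.

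What remains is that no section supplies the missing exception, and the cap on new toxicities holds on both readings. The tests between arms do not fully replace case-level judgement for rare events. With 20 per arm, two-sided Fisher p is 2 × C(20,4)/C(40,4) = 0.11 for 4 versus 0, and 2 × C(20,5)/C(40,5) = 0.047 for 5 versus 0.

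**Conclusion.** Wrong as written, minor severity. A toxicity of a new type cannot be rated Probable however strong the individual evidence; this does not depend on how Possible is read. Whether such an event is capped at Possible or has no rating does depend on that reading, as does the count of unrated combinations (6 or 9 of 24). The pre-dose defect assumes the literal text is applied.

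The consequence is confined to the descriptive tabulation by relationship and any informal use of the rating when association is judged. No estimate, test, error rate, sample size or reporting deadline changes.

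**What to change.** Reword the three definitions and the matching case report form instruction.

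- **Probable:** let the second condition be met if the event either "follows a known response pattern to the study drug" or "reappears on repeat exposure". Keep the other three conditions unchanged.
- **None:** onset before the first dose with no later worsening, or clearly related to other factors.
- **Possible:** every other event with onset or worsening after the first dose that does not meet Probable.

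Each event then has exactly one rating. Probable excludes None, because it requires both timing after dosing and no other reasonable explanation; Possible takes whatever is left. A new type of event that fits in time, has no other explanation and returns on re-exposure becomes Probable. If it only improves on stopping, it is Possible.

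Two alternatives are less good. Moving the known pattern into the list of supporting features would let a familiar event become Probable with no evidence from stopping or re-exposure. Making None the remainder would push late events of uncertain timing into None.

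The cost is a few lines of text. A few more events may be rated Possible or Probable.
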